
additional exploratory approaches (e.g., modified ITT models, per protocol analysis, and completer analysis) will be undertaken as indicated and a sensitivity analysis comparing these models to the ITT model will be completed.

**Power and Sample Size.** This study is largely focused on obtaining preliminary data to inform and power a larger randomized controlled trial to assess NAC for TUD. However, the proposed sample size (N=110) of this study will allow for adequate power to detect differences between treatment groups for the first two stated aims and hypotheses. This study is powered to assess the hypothesis that NAC, as compared to placebo, will promote greater abstinence from smoking during a 3-day quit attempt at the beginning of an eight week randomized controlled trial. In a pilot trial (N=16) investigating NAC as a cessation aid over three days of reinforced abstinence, [name] and colleagues (35) found that the majority of study participants given NAC achieved high rates of abstinence on the second and third days of reinforced abstinence (75% and 100%, respectively) following a target quit date. Conversely, those randomized to the placebo condition achieved lower rates of abstinence on the second and third days (12.5% and 25%, respectively). With a proposed sample size in the current study of 110 participants (55 randomized to each treatment assignment), this number will provide sufficient power (80%) with a type 1 error rate of 5% to detect abstinence rate differences of as low as 20% between those randomized to NAC versus placebo.

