Following the initial 3-day reinforced quit attempt, relapse rates will be examined to determine if NAC aids in relapse prevention as compared to placebo. Detectable relapse rates and associated hazard ratios (HR) based on the proposed sample size (N=110) are shown below in Table 1 based on varying relapse rates among the placebo and NAC groups. Including all randomized participants and assuming 70-90% of those randomized to placebo will relapse throughout the duration of the study, we will be sufficiently powered to detect relapse rates as high as 46-73% in those randomized to NAC (HR=1.8-2.0). Secondarily, we will assess relapse prevention among only those participants who achieved initial abstinence during the initial 3-day period. Assuming 30% of those randomized to placebo and 50% of those randomized to NAC will attain initial abstinence (low initial abstinence); we will have adequate power to detect relapse rates as high as 34-62% (HR=2.4-2.9) in the NAC group (assuming 70-90% relapse in the placebo group). If we achieve 50% and 75% initial 3-day abstinence in the placebo and NAC groups (high initial abstinence), we will have adequate power to detect relapse rates as high as 41-69% (HR=2.3-2.9) in the NAC group.

Placebo Relapse Rate	All Randomized Participants		Participants who achieve three day abstinence (ABS)			
	N=110		Low 3 day ABS; n=45		High 3 day ABS; n=70	
	Detectable NAC Relapse Rates	HR	Detectable NAC Relapse Rates	HR	Detectable NAC Relapse Rates	HR
70%	46%	1.98	34%	2.91	41%	2.25
80%	58%	1.86	46%	2.60	54%	2.09
90%	73%	1.76	62%	2.36	69%	1.95

*Table 1. Detectable rates of relapse and associated hazard ratios (HR).*

Additionally, assuming a conservative study attrition rate of 20%, a randomized sample of 110 participants (88 study completers) will provide sufficient power to detect a 23-29% difference in end-of-treatment (Week 8) abstinence between the two groups (assuming 10-30% abstinence rate in the placebo group). Therefore, 110 randomized participants will provide sufficient power to detect treatment differences for the first two stated hypotheses, and will provide effect sizes and estimates of variability for end-of-treatment abstinence at eight weeks to power a larger randomized controlled trial.

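### The unconditional claim of sufficient power for Aim 2 rests on unsourced placebo abstinence rates well above the only placebo data cited, and no scenario covers a low placebo rate with a high NAC rate

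*Combined protocol and SAP*

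**What the plan says.** Section A defines Aim 2 as time to relapse over eight weeks among those who maintain the initial 3-day abstinence. Statistical Analyses in section D repeats that population.

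Power and Sample Size states that the sample size "will allow for adequate power to detect differences between treatment groups for the first two stated aims and hypotheses". The design is described as follows: "With a proposed sample size in the current study of 110 participants (55 randomized to each treatment assignment"). Power of 80% and a type 1 error rate of 5% are given for Aim 1. For relapse the text says only that power is adequate or sufficient. Sidedness is not stated anywhere.

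Three relapse cases follow: all randomized participants (N=110), abstainers at 30% placebo and 50% NAC (n=45), and the high-abstinence case, "If we achieve 50% and 75% initial 3-day abstinence in the placebo and NAC groups (high initial abstinence"; n=70). The closing sentence of the section then says, with no condition, that 110 participants are enough for the first two hypotheses.

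The same section cites one source of 3-day data: "In a pilot trial (N=16) investigating NAC as a cessation aid over three days of reinforced abstinence". There the NAC group "achieved high rates of abstinence on the second and third days of reinforced abstinence (75% and 100%, respectively"), while "those randomized to the placebo condition achieved lower rates of abstinence on the second and third days (12.5% and 25%, respectively"). Day 1 rates, continuous 3-day rates and arm sizes are not given.

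**The concern.** A person abstinent on all three days is abstinent on Day 2. In the pilot sample, continuous 3-day abstinence was therefore at most 12.5% on placebo and at most 75% on NAC. Table 1 assumes placebo rates 2.4 and 4 times that placebo ceiling (30/12.5 and 50/12.5), gives no reason, and shows nothing lower.

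The two powered aims also pull against each other. The more NAC raises 3-day abstinence over placebo, the more unequal the groups become in the Aim 2 comparison. Table 1 raises the two rates together (30/50, then 50/75), so it never shows a low placebo rate beside a high NAC rate.

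Section E.4 says the trial will help show whether NAC is a cessation aid, a relapse-prevention aid, or both. If few placebo participants reach three days, a non-significant Aim 2 result could be taken as evidence against relapse prevention because the plan calls the comparison adequately powered.

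**Working it through.** **Inputs.** From Power and Sample Size and Table 1: 55 per arm; placebo relapse 70/80/90%; NAC relapse 41/54/69% in the high-abstinence column and 34/46/62% in the low one. From the pilot: Day 2 abstinence 12.5% placebo, 75% NAC. Assumptions: exponential relapse times, 5% type 1 error, and 80% as the meaning of adequate.

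**Table 1's own figures.**
- High column: 0.50 × 55 + 0.75 × 55 = 27.5 + 41.25 = 68.75, printed as 70.
- Low column: 0.30 × 55 + 0.50 × 55 = 16.5 + 27.5 = 44, printed as 45.
- HR = ln(1 − placebo relapse) / ln(1 − NAC relapse). At 70% and 41%: ln 0.30 / ln 0.59 = 2.28, against 2.25 printed. The other two rows give 2.07 and 1.97, against 2.09 and 1.95. Rounding of the relapse rates explains the differences.

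**Power formula (Schoenfeld).** Power = Φ(√(d·π(1−π)) · ln HR − z), where d is the expected number of relapses, π is the placebo share of abstainers, and z = 1.96 two-sided or 1.645 one-sided.

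Table 1's split, 28 vs 41, at 70%/41%:
- d = 28 × 0.70 + 41 × 0.41 = 36.4; π = 28/69 = 0.406.
- √(36.4 × 0.241) × 0.825 = 2.44, so two-sided power is Φ(0.48) = 69%.

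Pilot Day 2 rates: 0.125 × 55 = 6.9 and 0.75 × 55 = 41.25, so 7 vs 41, at 70%/41%:
- d = 7 × 0.70 + 41 × 0.41 = 21.7; π = 7/48 = 0.146.
- √(21.7 × 0.125) × 0.825 = 1.36, so two-sided power is Φ(−0.60) = 27%.

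**Results across the three placebo relapse rates.** The formula is approximate at such unequal splits, so the log-rank test was also simulated (4,000 to 6,000 runs per cell).

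| Placebo / NAC abstinence | Abstainers | Effects used | Two-sided, simulated | Two-sided, Schoenfeld |
|---|---|---|---|---|
| 50% / 75% (Table 1, high) | 28 vs 41 | high column | about 70–72% | 67–69% |
| 30% / 50% (Table 1, low) | 17 vs 28 | low column | about 70–72% | 66–67% |
| 30% / 75% | 17 vs 41 | high column | 58–60% | 51–53% |
| 20% / 75% | 11 vs 41 | high column | 47–50% | 38–40% |
| 12.5% / 75% | 7 vs 41 | high column | 38–41% | 27–29% |
| 12.5% / 75% | 7 vs 41 | low column | 52–57% | 37–41% |

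In the first two rows, simulated power reaches about 80% only with a one-sided 5% test. At 7 vs 41 the simulated figures are, if anything, generous: with equal relapse in both arms the test rejects about 6% of the time two-sided and 7–8% one-sided, against a nominal 5%.

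The loss at pilot rates comes from the imbalance. The total of 48 abstainers (7 + 41) exceeds the low scenario's 45.

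**Uncertainty of the pilot rate.** If 12.5% is 1 of 8 (equal arms are assumed), the exact 95% confidence interval is 0.3% to 52.7%.

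**A discrepancy in the same sentence.** For the high-abstinence case the text gives HR 2.3–2.9, whereas Table 1 prints 1.95–2.25.

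**The case against.** Several stronger readings are tempting, and the documents do not support them.

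- A reader might infer that the pilot caps placebo abstinence at 12.5%. The ceiling holds only within that sample, and the interval above includes both 30% and 50%.
- A reader might infer that Table 1 took its 75% from the pilot. The plan does not say so. The figure only equals the pilot's Day 2 NAC rate, itself an upper bound on 3-day abstinence.
- A reader might call Table 1 an arithmetic error. Its group sizes and hazard ratios reproduce to rounding, and the scenario sentences are worded as conditions. The dispute is over which scenarios to show.
- A reader might say that the pilot rates destroy a power that was otherwise present. At a two-sided 5% level it was already only about 70–72%.
- A reader might say that the whole relapse question would rest on about 7 placebo participants. The plan lists an all-randomized relapse analysis first, and that analysis does not depend on 3-day rates.

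The plan also has a fair defence. It does not adopt the pilot's effect. It sizes Aim 1 for a 20-point difference, which is exactly the 30% vs 50% scenario, and shrinking the effect from a 16-person pilot is reasonable. Both scenarios already have fewer placebo than NAC abstainers, so the tension between the aims is partly represented. The study is also described as largely preliminary.

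This defence narrows the point but does not remove it. The conditions on the scenarios do not carry over to the closing claim, which has none. The all-randomized analysis mixes cessation with relapse prevention, so it answers a different question from Aim 2 as written. An uncertain pilot rate is a reason to show a range that includes it.

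**Conclusion.** The concern holds as a gap between the claim and its support. The plan states sufficient power for Aim 2 without condition, but the design has it only if enough placebo participants reach three days of abstinence. The rates assumed for that are unsourced and lie above the only placebo data cited.

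For the high-abstinence effects with NAC at 75%, simulated two-sided power falls from about 70–72% at Table 1's 50% placebo rate to 58–60% at 30% and 38–41% at 12.5%. The conclusion therefore does not need the exact pilot value: power is short even at the plan's own lower placebo rate if NAC reaches 75%.

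This rests on exponential relapse times, 55 per arm, Table 1's relapse rates, and 80% as the target. Because sidedness is not stated, the size of the shortfall at Table 1's own splits is open. At the pilot split, power is well below 80% whether the test is one- or two-sided.

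**What to change.** In Power and Sample Size:

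1. State the sidedness, type 1 error and power behind Table 1.
2. Give the basis for the 30% and 50% placebo abstinence rates. Add at least one lower-placebo scenario, including the pilot Day 2 rates (12.5% and 75%; about 7 and 41 abstainers), labelled as uncertain.
3. Replace the unconditional claim for Aim 2 with a statement that power among abstainers depends on the number of placebo abstainers and may be well below 80%. Add that a non-significant result in this subset will be interpreted through the hazard ratio and its confidence interval, and not as evidence of no relapse-prevention effect.
4. Note that the all-randomized analysis does not depend on 3-day rates but addresses a different question from Aim 2 as written.
5. Reconcile the text's HR 2.3–2.9 for the high-abstinence case with Table 1's 1.95–2.25.

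The cost is an added table column and a few sentences, with no extra participants. The downside is that the stated Aim 2 power becomes less favourable.

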#### Statistical Analyses

Categorical clinical and demographic variables will be assessed by chi-square tests of independence, while continuous variables will be assessed using Student's *t*-test. In addition to baseline group differences, preliminary analysis of baseline characteristics with tobacco use outcomes of interest will examine significant correlates of abstinence in the study population. Characteristics found to be significantly associated with tobacco abstinence and relapse outcomes will be included as covariates in the initial stages of model development. The primary measure of interest will be the proportion of biochemically confirmed and self-reported 3-day abstinence (defined as twice per day breath CO measures of  $\leq 6$  ppm or a 75% reduction from the participant's averaged baseline and Day 0 CO samples). The proportion of participants achieving 3-day abstinence will be compared between NAC and placebo treatment groups using logistic regression models (Specific Aim #1). Secondarily, there is great interest in determining if those who achieved 3-day abstinence under NAC treatment were less likely to relapse over the course of eight weeks compared than those who achieved abstinence under placebo treatment (Specific Aim #2). Daily smoking diary data will be used in conjunction with weekly breath CO measures to determine if and when relapse to regular smoking returned during the eight weeks of treatment with the study drug. Based on recommendations for defining treatment failure, relapse will be defined as smoking during seven consecutive days or smoking at least once over two consecutive weeks (54). This definition will account for regular and irregular smoking over the course of the eight-week intervention phase. Cox proportional hazards models will be developed to assess the efficacy of NAC in prolonging abstinence and preventing relapse. Additionally, end of study 7-day point prevalence abstinence will be assessed through the proportion of self-reported and biochemically confirmed 7-day abstinence. Biochemical confirmation for end-of-study abstinence is defined as a negative daily breath CO measures ( $\leq 6$  ppm or 75% reduction from baseline) and a negative urine cotinine measure ( $<80$  ng/mL). The main effect of NAC versus placebo on the proportion of abstinent participants will be assessed using logistic regression models. All stated models will be computed both unadjusted and adjusted for significant covariates and confounders found in the preliminary analysis. All randomized participants will be included in the primary analysis (intent-to-treat; ITT) and participants will be deemed not-abstinent at any missed visit or missing CO measure (drop-out/loss-to-follow up included). In addition to the primary ITT analyses,

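### Table 1's Aim 2 relapse power makes no stated allowance for the 20% attrition used for Week 8; depending on how drop-outs are coded, the cost is nil, about 3 to 5, about 9 to 10, or about 8 to 15 points of power.

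*Combined protocol and SAP*

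**What the plan says.** In Power and Sample Size, the Aim 1 sentence gives "sufficient power (80%) with a type 1 error rate of 5" per cent for "110 participants (55 randomized to each treatment assignment"). Sidedness is not stated.

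For Aim 2: "Detectable relapse rates and associated hazard ratios (HR) based on the proposed sample size (N=110) are shown below in Table 1". The all-randomized column is introduced by "assuming 70-90% of those randomized to placebo will relapse throughout the duration of the study", after which "we will be sufficiently powered to detect relapse rates as high as 46-73% in those randomized to NAC (HR=1.8-2.0"). The two other columns cover participants who achieve 3-day abstinence, with n=45 and n=70. No power percentage is printed for Aim 2.

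The paragraph after Table 1 turns to Week 8 abstinence: "assuming a conservative study attrition rate of 20%, a randomized sample of 110 participants (88 study completers"), with 10-30% abstinence on placebo. It ends by claiming sufficient power for the first two hypotheses.

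The Statistical Analyses section keeps everyone randomized in the primary analysis and says "participants will be deemed not-abstinent at any missed visit or missing CO measure (drop-out/loss-to-follow up included"). Relapse is defined separately, as smoking on seven consecutive days or at least once in each of two successive weeks or similar irregular smoking over two weeks, and is analysed with Cox models. No sentence says how drop-outs enter those models.

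**The concern.** Aim 2 follows participants over the same eight weeks as the Week 8 endpoint, so it faces the same attrition. Its assumed placebo relapse of 70-90% is the numerical complement of the 10-30% placebo abstinence that the plan applies to 88 completers. One set of assumptions is therefore used with 20% attrition for one endpoint and with none shown for the other.

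If attrition belongs in both, the closing claim of sufficient power is too favourable for Aim 2. The study is largely meant to supply figures for powering a larger trial, so the detectable effects in Table 1 should mean what a reader takes them to mean.

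**Working it through.** **Inputs.** Rates and hazard ratios (HRs) are from Table 1. Arms are 55/55. The low-abstinence subset is 0.30×55 = 16.5 placebo and 0.50×55 = 27.5 NAC, total 44 (table: 45). The high-abstinence subset is 0.50×55 = 27.5 and 0.75×55 = 41.25, total 68.75 (table: 70). These sizes are randomized numbers times abstinence rates, with no deduction for attrition. The 5% error rate is carried over from the Aim 1 sentence. Attrition is 20% in each arm.

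**Formulas.** HR = ln(1−p_placebo)/ln(1−p_NAC). Events D = n_placebo·p_placebo + n_NAC·p_NAC. Power = Φ(√(D·a(1−a))·ln HR − z), where a is the NAC share and z = 1.960 two-sided or 1.645 one-sided.

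**Reproducing the plan.** The HRs follow from the rates within rounding (70% v 46%: ln 0.30/ln 0.54 = 1.954, printed 1.98). An 80% power level does not reproduce under one convention. For 70% v 46%, D = 55×1.16 = 63.8, √(63.8×0.25)×ln 1.954 = 2.676, and 2.676 − 1.960 = 0.716, giving 76.3% two-sided. One-sided Freedman gives 79-80% in the subsets but about 83% for N=110. Two-sided log-rank simulation gives 76-77% (all), 70-72% (low) and 69-71% (high).

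**Adding 20% attrition, same cell.**
- Censored: expected event proportion per arm = l/(l+m)·(1−e^−(l+m)), with l = −ln(1−p) and m = −ln 0.8. D = 58.2; power 72.4%.
- Removed, as for Week 8: D = 0.8×63.8 = 51.0; power 66.7%.
- Counted as relapse: p′ = 0.2 + 0.8p gives 76% v 56.8%, HR 1.70, D = 55×1.328 = 73.04; power 62.1%.

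Two-sided power (%) over the three rows of each column:

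| Column | No attrition | Censored | Removed | Counted as relapse |
|---|---|---|---|---|
| All, 55/55 | 76.2-76.8 | 72.4-73.2 | 66.7-67.3 | 62.1-67.7 |
| Low, 16.5/27.5 | 65.3-65.9 | 61.3-62.4 | 55.8-56.4 | 50.3-56.9 |
| High, 27.5/41.25 | 66.1-68.1 | 62.3-64.1 | 56.6-58.5 | 53.8-58.9 |

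The falls are 3.3-4.1 points (about 3 to 5 as a rounded bracket), about 9.5, and 8.5-15.1. Simulation with drop-outs counted as relapse and spread over the eight weeks gives about 8.5-16 points; with all drop-out at the start, about 21-28.

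One-sided, all randomized starts at about 85% and becomes 82% (censored), 77-78% (removed) or 73-78% (relapse). The subsets start at 76-78% and become 73-75%, 68-70% and 63-71%.

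**If the rates already include drop-outs.** Relapse among those retained is (p−0.2)/0.8. In the 70% row:
- All: 62.5% v 32.5%, HR = ln 0.375/ln 0.675 = 2.5 (printed 1.98).
- Low: 62.5% v 17.5%, HR 5.1 (printed 2.91).
- High: 62.5% v 26.25%, HR 3.2 (printed 2.25).

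**Cross-check on Week 8.** With 44 per arm, 30% v 59% has 79.2% power two-sided, against 87.5% with 55 per arm. The plan's 29-point difference therefore does use the attrition-reduced sample.

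**The case against.** A reader might infer that the plan assumes complete follow-up for Aim 2 and that its own drop-out rule lowers every Aim 2 power figure by 8 to 15 points. The documents do not support that.

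- The all-randomized rates are expressed among those randomized, and drop-outs are deemed not abstinent. The rates could therefore already count drop-outs as relapse, in which case 110 is the right denominator and power does not fall.
- The drop-out rule sets abstinence status at a visit. Relapse is a separate endpoint, and carrying the rule into the Cox model is plausible but unstated.
- No Aim 2 power percentage is printed, so none can be said to fall. Most of the subsets' shortfall against 80% comes before attrition.
- The 20% is a whole-study figure that the plan calls conservative. The subsets already exclude anyone lost in Days 1-3, and equal loss in both arms is also assumed.
- The same rule keeps all 110 in the Week 8 analysis, so the 88-completer calculation is itself a departure from it.
- Enrolment of 120 is planned. That margin is for data-integrity problems, and it lifts the all-randomized, counted-as-relapse figures only from 62-68% to 66-71% two-sided.

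These points stand as limits on the size. They do not remove the gap. Because the complementary abstinence rates are applied to 88 completers, reading the relapse rates as already absorbing drop-outs is possible but not the natural reading. Even on that reading, the table does not show the effect needed among retained participants.

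**Conclusion.** The point holds in conditional form. Table 1 makes no stated allowance for attrition that the next paragraph treats as expected over the same period. The loss of power runs from none (drop-outs already in the rates), through about 3 to 5 points (censored) and about 9 to 10 (removed), to about 8 to 15 (counted as relapse).

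If drop-outs are removed or counted as relapse, no cell reaches 80%, one- or two-sided. The cells that stay above 80% are in the all-randomized column, tested one-sided, with drop-outs censored or already included. The closing claim of sufficient power for Aim 2 is therefore not supported as written.

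This rests on the Schoenfeld approximation, equal 20% attrition in both arms, and the same 20% applied to the 3-day-abstinent subsets, which is an assumption. The base below 80% two-sided is a separate matter.

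**What to change.** Recompute Table 1 and the HR ranges in the text with the 20% attrition already assumed. In the table note, state three things: how drop-outs are coded in the Cox model (the not-abstinent rule as default, censoring as a sensitivity case), whether the tabulated rates include drop-outs, and whether the test is one- or two-sided. Amend the closing sentence on Aim 2 to the restated figures. While doing so, reconcile the high-abstinence HR range, which the text gives as 2.3-2.9 and Table 1 as 1.95-2.25.

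As a guide to the size of the change: with drop-outs counted as relapse and each cell held at its present power, the detectable NAC relapse among retained participants becomes 41/54/71% instead of 46/58/73% (all), 26/40/58% instead of 34/46/62% (low) and 35/50/66% instead of 41/54/69% (high).

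The cost is recalculation and protocol wording, with less favourable detectable effects on paper. No extra participants are needed.
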